Following the attainment of stability, YMRS total score \leq 12 and MADRS total score \leq 12 and CGI-S \leq 3 must be maintained for an additional 8 weeks, with the exception of allowing 1 excursion (YMRS > 12 and/or MADRS > 12). If an excursion occurs, the YMRS and MADRS scores must return to the remission threshold (ie, \leq 12) at the subsequent visit. The excursion (YMRS > 12 and/or MADRS > 12) may occur at any time during the 8-week stability period with the exception of Visit 12/End of OL, but must be followed by a return to remission threshold at the next visit. In the event the excursion occurs in the 8th week of stability but prior to Visit 12/End of OL, patients should be assessed at the following visit to confirm whether randomization criteria have been met. Previously stabilized patients whose efficacy scores increase to YMRS \geq 17, MADRS \geq 20, or CGI-S \geq 4 during OL treatment will be discontinued from the study. Once stabilization has occurred and been maintained as described above, the patient will be randomized.

Patients who meet remission and stability criteria and subsequent randomization criteria will be eligible for early randomization beginning at Week 12 (Visit 10) and will move forward to the DB treatment period without requiring all visits in the OL treatment period.

If no tolerability issues arise, all patients will receive at least 6 weeks of OL treatment. Some patients will be discontinued from the study after 6 or 8 weeks of OL treatment if remission or stability criteria, respectively, have not been achieved.

Randomization/DB Treatment Period: OL patients who are able to maintain stability criteria for at least 8 weeks with no more than 1 excursion above the remission threshold will be randomized 1:1:1 to receive cariprazine at the same dose (3.0 mg/d), cariprazine at a reduced dose (1.5 mg/d), or placebo for up to 39 weeks. Patients will continue to receive study drug until a relapse event (manic or depressive) occurs or until completion of the 39 weeks of randomized treatment. Relapse will be defined as the occurrence of any 1 of the following:

- YMRS total score ≥ 17
- MADRS total score ≥ 20
- CGI-S ≥ 4

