8.9 Withdrawal Criteria

It is the right and the duty of the investigator or subinvestigator to stop treatment in any case in which emerging effects are of unacceptable risk to the individual patient. In addition, the investigator or subinvestigator is to stop treatment of any patient with unmanageable factors that may interfere significantly with the trial procedures and/or the interpretation of results.

A patient must be discontinued from the study for any of the following reasons:

1. The patient fails to achieve remission by Week 6 or stability by Week 8 of the OL treatment period;

- 2. After stability criteria (Section 4.5) have been met, if there is a lack of ongoing stability as evidenced by an excursion event of YMRS total score of \geq 17 and/or MADRS total score of \geq 20, or CGI-S \geq 4;
- 3. The patient initiated treatment with a mood stabilizer, antidepressant, antipsychotic agent, or with a benzodiazepine that exceeds the protocol-specified allowance or duration (ie, more than 2 mg/d of lorazepam equivalent or for more than 3 consecutive days) to treat worsening mood symptoms;
- 4. The patient required or initiated hospitalization for his/her psychiatric symptoms (excluding the discretionary hospitalization stay which is to end no later than Visit 3 [Day 8] of the OL treatment period or extension of the initial hospitalization described in this protocol);
- 5. At the end of the OL treatment period, the patient does not meet all criteria to enter the DB treatment period (eg, patient is unable to tolerate cariprazine 3.0 mg/d);
- 6. Positive UDS after enrollment, confirmed by retest at next scheduled visit; for exceptions see Exclusion Criterion 6(b) and Section 4.8.3;
- 7. The patient meets the criteria for relapse of a mood episode during the DB treatment period;
- 8. The patient experiences 1 of the following elevated liver enzyme conditions, which is confirmed by repeat testing:
 - ALT or AST $> 3 \times$ ULN and total bilirubin $> 2 \times$ ULN,
 - ALT or AST $> 8 \times ULN$,
 - ALT or AST $> 5 \times ULN$ for more than 2 weeks,
 - ALT or AST > 3 × ULN with the appearance of jaundice, worsening of fatigue, nausea, vomiting, right upper quadrant pain or tenderness, fever, rash, or eosinophilia.
- 9. The patient has an absolute neutrophil count of < 1000 per mm³ and, after repeat testing within 24 hours of awareness, the values are not normalized or are not increasing;
- 10. A female patient becomes pregnant during treatment.

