7.0 STUDY PATIENTS

7.1 PATIENT DISPOSITION

The OLTP starts with the first dose of OLTP and ends with one of the following: the last scheduled assessment at Visit 12 (Week 16) or early termination (ET) before Visit 12 for patients who do not enter the DBTP; or 1 day before the date of the first dose of DBTP (or the date of the first dose of the DB IP if the last scheduled assessment date in the OLTP is on the date of the first dose of the DBTP) for patients who enter the DBTP.

The DBTP starts with the first day of randomization and ends with the last scheduled assessment at Visit 31 (Week 55) or ET.

The SFU period starts one day after the end of the previous period and ends with the last available assessment. For patients without Visit 32 (Week 57) or Visit 34 (Week 59) assessment, the SFU period would not be derived.

Screen-failure patients (ie, patients screened but not included in the OL Safety Population) and the associated reasons for failure will be tabulated overall for the Screened Population.

The number and percentage of patients in the Screened, OL Safety and OL ITT Populations will be summarized overall and by study center. The number and percentage of patients in the Randomized, DB Safety, and DB ITT Populations will be summarized overall by treatment group and by treatment group and study center.

The number and percentage of patients in the OL Safety Population, who prematurely discontinued from the OLTP, who completed the OLTP, who entered the DBTP, and who entered the SFU period will be summarized overall and by reasons for premature discontinuation as recorded on the OL disposition page of the electronic case report forms (eCRF).

Similarly, the number and percentage of patients in the DB Safety Population who completed the DBTP, who prematurely discontinued from the DBTP, and who entered the SFU period will be summarized overall, by DBTP treatment group and by reasons for premature discontinuation as recorded on the DB disposition page of the eCRF. Patients who relapse during the DBTP will also be summarized as completing the study.

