10.3 ADDITIONAL EFFICACY PARAMETERS

The overall relapse rate, as well as the relapse rates for sub-categories of interest including modified manic episode and modified depressive episode will be presented.

Time to early discontinuation with any reason (including relapse) during the DBTP for the DB ITT population will be analyzed using the same method used to analyze the primary efficacy variable.

For the following continuous efficacy variables, the change from baseline refers to the change from OL baseline during the OLTP, and the change from DB baseline during the DBTP, unless stated otherwise.

For Open-label Treatment Period

- Change from baseline in YMRS total score by visit
- Change from baseline in MADRS total scores by visit
- Change from baseline in CGI-S score by visit
- CGI-I score by visit
- Change from baseline in PSP total score and sub-domain score by visit

For Double-blind Treatment Period

- Change from DB baseline in YMRS total score by visit
- Change from DB baseline in MADRS total score by visit
- Change from DB baseline in CGI-S score by visit
- CGI-I score by visit
- Change from DB baseline in PSP total score and sub-domain score by visit

Descriptive statistics (n, mean, standard deviation, median, Q1, Q3, minimum and maximum) for additional efficacy parameters will be provided by visit for the OL ITT population and the DB ITT population using both last-observation-carried forward (LOCF) and observed cased (OC) approaches. LOCF approach will be used to impute missing postbaseline values. Imputation of missing values will be done for the OLTP and the DBTP separately.

For the DBTP, the additional efficacy parameters will be analyzed by using a mixed-effects model for repeated measures (MMRM) with treatment group, region (US and non-US), modified index episode strata (manic or depressive), visit, and treatment group-by-visit interaction as fixed effects and the baseline value and baseline-by-visit interaction as the covariates. An unstructured covariance matrix will be used. The Kenward-Roger approximation ([Kenward and Roger, 1997](#)) will be used to estimate denominator degrees of freedom. The analysis will be performed based on post-DB baseline scores using only the OC without imputation of missing values. Least squares mean and their standard errors based on the MMRM analysis will be plotted by treatment group and visit.

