proc sort data=a1 out=a2;
  by randdt;
run;

data b2;
  set a2 end=eof;
  retain franddt;
  format franddt yymmdd10.;
  if _n_=1 then do;
    franddt = randdt;
    set b1;
  end;
  if eof then do;
    lranddt = randdt;
    ta = lranddt - franddt; * duration of enrollment period;
    tfmin = %eval(&fllow.*7);
    tfmax = %eval(&fhigh.*7);
    output;
  end;
  keep franddt ta tfmin tfmax;
  label franddt="Randomization Date for First Randomized Subject"
    ta="Duration of Enrollment Period (days)"
    tfmin="Minimum Follow-up Time (days)"
    tfmax="Maximum Follow-up Time (days)";
run;

proc print data=b2 label;
  var franddt ta tfmin tfmax;
run;

data a3;
  set a1;
  if _n_=1 then set b2;
  e = randdt - franddt; * enrollment time for the current subject;
  *if compynfl="Y" or index(upcase(trmspc),"26 WEEK")>0 then do; /* completed the study */
  if compdbfl="Y" then do;
    tf = durdb;
    complete=1;
  end;
  else do; * relapsed or discontinued for other reasons;
    tf = min(ta - e + tfmin, tfmax);
    complete=0;
  end;
run;

data raw1;
  merge a3
    ad.adtte(keep=aval cnsr paramn subjid trt03pn where=(paramn=0)); ***paramn=0 corresponds
  to time to relapse***;
  by subjid;
  status=(cnsr=0);
  rename subjid=subj trt03pn=treated aval=time tf=followup;
  keep subjid trt03pn cnsr status aval complete tf episode;
run;

* check number of events per treatment group;
proc freq data=raw1;
  tables treated*status/norow nocol nopercents;
run;

ods listing close;

* examine Bayesian analysis results to determine thinning;
proc phreg data=raw1;
  class episode;
  model time*status(0)=episode region treated;
  bayes piecewise=hazard;
run;

* ==> thin=10 is enough to achieve approx. indep. posterior samples;
%let thin=10; * thinning;
%let ninterval=8; * number of time intervals for piecewise exponential;
%let nimps=200; * number of imputations;
%let seed=314;

```

```

* obtain sample size in raw data;
proc sql noprint;
    select count(*) into :n from raw1;
quit;

data raw;
    set raw1(drop=subj);
    subj = _n_;
run;

options nonotes nosource;
ods noreresults;
ods html close;
ods graphics off;

data bootid;      * dummy data set to store bootstrapped subject numbers;
    seed=123;
    do boot=0 to 100;
        do i=1 to &n;
            if boot=0 then subj=i;
            else do;
                call ranuni(seed, u);
                subj=ceil(&n*u); * bootstrapped subject number;
            end;
            output;
        end;
    end;

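### SAP 7.1 counts patients who relapse as completing the study, so the by-arm disposition table pools the primary failure event with relapse-free completion

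*SAP*

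**What the plan says.** SAP 7.1 (Patient Disposition) tabulates, for the DB Safety Population, patients who completed the double-blind period and patients who left it prematurely, "by DBTP treatment group and by reasons for premature discontinuation as recorded on the DB disposition page of the eCRF". It then adds: "Patients who relapse during the DBTP will also be summarized as completing the study".

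Three other places give relapse a different status:

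- Protocol 8.9 opens its list with "A patient must be discontinued from the study for any of the following reasons", and item 7 reads "The patient meets the criteria for relapse of a mood episode during the DB treatment period".
- SAP 10.3 defines an additional endpoint as "Time to early discontinuation with any reason (including relapse) during the DBTP for the DB ITT population".
- In SAP Appendix II, the branch of the sample code that sets the completer flag to 0 carries the comment "else do; * relapsed or discontinued for other reasons".

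Two places point the other way. Protocol Section 3 (Study Design) treats relapse as a planned end of treatment: "Patients will continue to receive study drug until a relapse event (manic or depressive) occurs or until completion of the 39 weeks of randomized treatment". Protocol 8.8, which lists reasons for premature discontinuation, does not name relapse. SAP 18.0 (changes from the protocol) does not mention the disposition rule.

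**The concern.** Relapse is the primary failure event. SAP 7.1 adds it to the favourable category of a by-arm table, and adds more of it in whichever arm relapses more often. The resulting percentage answers neither how many patients stayed on randomized treatment for 39 weeks nor how many left for reasons other than relapse, unless the reader knows the rule. Readers of a randomized-withdrawal trial use this table to judge attrition. As written, the completion row and the time-to-discontinuation analysis in SAP 10.3 would describe the same patients in opposite terms.

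**Working it through.** **Inputs (SAP 14.0).** Placebo relapse by Week 39 is 35%. The hazard ratio is 0.42. Discontinuation for other reasons is 26%, not split by arm. There are 126 patients per arm and a fixed 39-week follow-up.

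**Model (assumed).** Constant competing hazards over 39 weeks, with the same dropout hazard in every arm:

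- placebo relapse: −ln(0.65) = 0.431
- cariprazine relapse: 0.42 × 0.431 = 0.181
- dropout: −ln(0.74) = 0.301

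For relapse hazard l and dropout hazard d:

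- P(relapse) = l/(l+d) × (1 − exp(−(l+d)))
- P(dropout) = d/(l+d) × (1 − exp(−(l+d)))
- P(39 weeks without relapse) = exp(−(l+d))

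**Check against the plan's own figure.** P(relapse) is 0.3055 on placebo and 0.1436 on each cariprazine arm. Expected events are 126 × (0.3055 + 2 × 0.1436) = 74.7, against about 75 in SAP 14.0. The inputs are therefore read consistently with the sample-size section.

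**Disposition under the two definitions.** Completion under SAP 7.1 is 1 − P(dropout), because relapsers are added to completers.

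| | Placebo | Each cariprazine arm |
|---|---|---|
| Relapse | 30.5% | 14.4% |
| Dropout for other reasons | 21.4% | 23.9% |
| 39 weeks without relapse | 48.1% (61/126) | 61.8% (78/126) |
| Completed, SAP 7.1 rule | 78.6% (99/126) | 76.1% (96/126) |
| Early discontinuation including relapse (SAP 10.3) | 51.9% | 38.2% |

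The cariprazine-minus-placebo difference is 61.8 − 48.1 = +13.7 points for relapse-free completion and 76.1 − 78.6 = −2.5 points under SAP 7.1. Placebo comes out slightly higher because relapse removes patients before they can drop out. If 26% is instead the observed dropout proportion in each arm, SAP 7.1 gives 74% in every arm whatever the relapse rates.

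**Sensitivity to unequal dropout (splits assumed; the documents give none).**

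| Dropout, placebo / cariprazine | Completed, SAP 7.1: placebo vs cariprazine | Relapse-free at Week 39: placebo vs cariprazine |
|---|---|---|
| 20% / 26% | 83.6% vs 76.1% (−7.5) | 52.0% vs 61.8% (+9.8) |
| 26% / 26% | 78.6% vs 76.1% (−2.5) | 48.1% vs 61.8% (+13.7) |
| 30% / 26% | 75.3% vs 76.1% (+0.8) | 45.5% vs 61.8% (+16.3) |
| 35% / 26% | 71.1% vs 76.1% (+5.0) | 42.3% vs 61.8% (+19.5) |
| 40% / 20% | 66.9% vs 81.6% (+14.7) | 39.0% vs 66.8% (+27.8) |

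In every row the SAP 7.1 difference is less favourable to cariprazine than the relapse-free difference. The distance between them is the between-arm difference in relapse proportions (about 13 to 17 points here).

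**Appendix II.** The completer flag is read from the disposition status field, so coding relapsers as complete would contradict the code comment. In both imputation steps, however, subjects with an event keep their observed time and status. The flag therefore changes no imputed value for a relapser.

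**The case against.** The strongest defence is that relapse is a planned end of follow-up. SAP 14.0 and Protocol 7.5 list dropout, relapse and 39 weeks as three separate ends, and the 26% covers only other reasons. Item 7 of Protocol 8.9 says the patient must leave; it does not label that exit premature. Counting patients who reach the endpoint as completers is a recognised convention, and SAP 10.3 says openly that its all-cause endpoint includes relapse. That stands as a reason not to call relapsers premature discontinuations. It does not justify merging them with 39-week completers without a label, because the plan's own three-way split is what the table drops.

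A second defence is that nothing is lost: relapse rates, Kaplan-Meier curves, time to all-cause discontinuation and exposure are all reported by arm. This largely stands. The table cannot be unpicked exactly, though, because disposition uses the DB Safety Population by treatment received, while the efficacy analyses use the DB ITT population as randomized.

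Third, table specifications sit in a separate document, and the word *also* in SAP 7.1 could allow a distinct relapse row. It could, but SAP 7.1 does not specify one.

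A reader might go further and infer that the plan conceals the retention difference or reverses it. The documents do not support that. The retention comparison is available in SAP 10.3, and the reversal is about 3 patients in 126 under an assumed equal dropout hazard.

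**Conclusion.** The inconsistency is in the current text and is worth correcting. Following SAP 7.1 as written, the by-arm completion figure combines relapse with relapse-free completion. Under the plan's inputs, constant hazards and equal dropout, that means about 79% vs 76% (placebo vs cariprazine) shown as completing, against about 48% vs 62% reaching Week 39 without relapse. The direction of the SAP 7.1 difference depends on the dropout split, which the documents do not give. With much higher placebo dropout, cariprazine still looks better retained, but by less than it is.

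The consequence is confined to a descriptive table. It would be wrong to infer any effect on the primary log-rank test, alpha, power or the Appendix II imputations; none of them uses this classification in a way that changes a result.

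**What to change.** In SAP 7.1, replace the sentence on relapsers with three mutually exclusive double-blind outcomes by arm:

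1. completed 39 weeks without relapse;
2. ended because of relapse;
3. discontinued for another reason, by eCRF reason.

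Reconcile the terms with Protocol 8.9 item 7 and SAP 10.3, so that relapse has one stated status for reporting, and make the Appendix II completer flag agree with its comment. If the sponsor wishes to keep a completed-the-study figure that includes relapse, show it only as a labelled subtotal beneath the three rows.

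The cost is SAP wording and one disposition derivation; no new data are needed. The downside is that the headline completion percentage falls in every arm.

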7.2 PROTOCOL DEVIATIONS

The number and percentage of patients with important protocol deviations will be summarized overall for the OLTP, and by treatment group for the DBTP. Supportive listings will also be provided. At a minimum, deviations related to the following categories will be included:

- Inclusion or exclusion criteria
- Withdrawal criteria
- Treatment or dose
- Concomitant medications

These and any additional important protocol deviations will be reviewed and documented before database lock and unblinding of treatment codes.

8.0 DEMOGRAPHICS AND OTHER BASELINE CHARACTERISTICS

Demographic parameters, including age; age group; region; race; ethnicity; sex; weight; height; and body mass index (BMI), calculated as weight [kg]/(height [m])² will be summarized descriptively overall for the OL Safety and OL ITT Populations and by treatment group for the DB Safety and DB ITT populations.

The baseline efficacy variables for OLTP, which is defined as the last available assessment at or prior to the first dose of OL IP, will be summarized descriptively overall for the OL ITT Population. The baseline efficacy variables for DBTP, which is defined at the last available assessment at or prior to the first dose of DB IP, will be summarized by treatment for the DB ITT Population.

The medical and surgical history, psychiatric disorders, and nondrug psychiatric treatment, will be summarized descriptively overall for the OL Safety Populations and by treatment group for the DB Safety Populations.

Continuous variables will be summarized by number of patients and mean, SD, median, Q1, Q3, minimum, and maximum values. Categorical variables will be summarized by number and percentage of patients.

Prior medication is defined as any medication started before the date of the first dose of OL IP. *Concomitant medication* during the OLTP is defined as any medication taken on or after the date of the first dose of OL IP during the OLTP. *Concomitant medication* during the DBTP is defined as any medication taken on or after the date of the first dose of DB IP during the DBTP.

The use of prior and concomitant medications during the OLTP will be summarized by the number and percentage of patients receiving each medication within each therapeutic class for the OL Safety Population. The use of concomitant medications during the DBTP and SFU period will be summarized by treatment group by the number and percentage of patients receiving each medication within each therapeutic class for the DB Safety Population. Multiple medication use by a patient will only be counted once.

The use of rescue medications during the OLTP and during the DBTP will be summarized by treatment group and generic terms for the following rescue medication categories in the safety population:

- Insomnia
- Extrapyramidal symptoms (EPS) or akathisia
- Agitation, Restlessness, and Hostility

Cariprazine
RGH-MD-25 – Statistical Analysis Plan
Amendment #3 – 23 November 2022

The *WHO Drug Dictionary Enhanced*, version March 2017 or newer, will be used to classify prior and concomitant medications by therapeutic class and drug name.

9.0 EXTENT OF EXPOSURE AND TREATMENT COMPLIANCE**9.1 EXTENT OF EXPOSURE**

Exposure to the OL IP for the OL Safety Population will be summarized for treatment duration, calculated as the number of days from the date of the first dose of OL cariprazine taken to the date of the last dose taken during the OLTP, inclusive. Descriptive statistics (n, mean, standard deviation, median, Q1, Q3, minimum and maximum) will be presented.

Exposure to the DB IP for the DB Safety Population during the DBTP will be summarized for treatment duration, calculated as the number of days from the date of the first dose of DB IP to the date of the last dose of DB IP, inclusive. Descriptive statistics (n, mean, standard deviation, median, Q1, Q3, minimum, and maximum) will be presented by treatment group.

Exposure to cariprazine during the entire study (OLTP and DBTP) will be summarized by intervals for the OL Safety Population. Descriptive statistics (n, mean, standard deviation, median, Q1, Q3, minimum, and maximum) will be presented.

By design, patients will take a fixed dose of cariprazine and there is no titration period during the DBTP. Mean daily dose, final dose will not be provided during the DBTP.

Patient-years, defined as exposure to the IP in years, will be summarized for the OLTP for the OL Safety Population. Patient-years will also be summarized by treatment group for the DBTP for the DB Safety Population. Patient years of exposure to cariprazine during the entire study (OLTP and DBTP) will also be summarized for the OL Safety Population.

